7.3.3.2 Sensitivity Analyses for Key Secondary endpoints

An MI approach identical to that used for the sensitivity analysis for the primary endpoint will be applied for each key secondary endpoint. As with the primary, a full set of data will be imputed for all visits including Week 52 and the analyses will report results for both the Week 13 and Week 52 time points.

7.3.3.3 Other Secondary

All endpoints, including the primary and key secondary endpoints, will be summarized by treatment group and by time point. The differences of other secondary endpoints between the SI-6603 and control groups will be analyzed at each time point they are collected as below.

- A similar longitudinal analysis model will be used as described in the primary efficacy analysis for the analysis of change from baseline in pain intensity scores, function scores, QOL scores, and volumes (intervertebral disc and herniation), by including the corresponding baseline value as the fixed effect instead of the baseline worst leg pain score.
- Percentage change from baseline in intervertebral disc and herniation volumes will be summarized in a line graph with error bars.
- Neurologic status as determined by neurological examinations will be compared between treatments with a difference in proportions Z test. In the case of low counts (<5 expected in a cell), a Fisher's exact test will be used. Outcomes will include SLR test, sensation, muscle strength, and deep tendon reflex. Counts and percentages in each category will be presented along with 95% confidence intervals, the difference in the percentages and its 95% Wald CI. Percentages will be reported out of non-missing values.
- For the global assessments of PGIC score and CGIC score, responder analysis with the two best categories as "responder" will be compared between treatments with a difference in proportions Z test. In the case of low counts (<5 expected in a cell), a Fisher's exact test will be used. Counts and percentages in each category for the PGIC and CGIC will be presented as well as the responder/non-responder counts and percentages along with 95% confidence intervals, the difference in the percentages of responders and its 95% Wald CI. Subjects with missing values will be considered non-responders.
- Scores on the WPAI will be analyzed with the analysis of covariance model including the baseline value and duration of leg pain as covariates.
- The incidence of rescue medication use will be compared between treatments with a difference in proportions Z test. In the case of low counts (<5 expected in a cell), a Fisher's exact test will be used. The amount of rescue medication use will be analyzed with the Wilcoxon rank sum test.

- Cumulative distribution of percentage change from baseline in worst leg pain and ODI will be generated, and differences between the SI-6603 and control groups in the percentages of subjects experiencing a $\geq 30\%$ and $\geq 50\%$ improvement in worst leg pain score will be compared between treatments with a difference in proportions Z test. In the case of low counts (< 5 expected in a cell), a Fisher's exact test will be used. Additionally, the difference in the percentages of responders and its 95% Wald CI will be reported. Subjects with missing values will be considered non-responders/not having improvement.
- For the analysis of the percentages of responders by composite definition, differences between the SI-6603 and control groups in the percentages of positive responders will be compared between treatments with a difference in proportions Z test. In the case of low counts (< 5 expected in a cell), a Fisher's exact test will be used. Counts and percentages of responders will be presented along with 95% confidence intervals, the difference in the percentages and its 95% Wald CI. See section [7.3.3.4](#) for the definition of composite responder.
- The number of subjects with recurrence of LDH, percentages and differences between the SI-6603 and control groups in the percentages will be reported. See section [7.3.3.5](#) for the definition of recurrence of LDH.
- Time to post-treatment surgery for LDH will be evaluated by survival analysis using Kaplan-Meier methodology and the log-rank test. Counts and percentages of subjects with post-treatment surgery will be reported as well as medians and quartiles of the time to surgery (if they are defined). Additionally, the number and percentage of subjects with post-treatment surgery for LDH will be reported and compared between treatment groups with a Fisher's exact test. The difference in the percentages of responders and its 95% Wald CI will also be reported.
- Time to post-treatment surgery for LDH will be summarized in a Kaplan-Meier plot.

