3.8 Study Design Schematic

4 STUDY POPULATION

4.1 Inclusion Criteria

Subjects will be allowed to participate in this study only if they meet all of the following criteria:

1. Subjects who have given their written informed consent to participate in the clinical study based on voluntary agreement after a thorough explanation of subject participation is provided to them. Subjects should be willing and able to provide written informed consent, adhere to the study visit schedule, and answer the questions on subject-completed assessments.
2. Male or female subjects 30 to 70 years of age, inclusive, at the time of informed consent.
3. Subjects with contained posterolateral LDH at either L4-L5 or L5-S1 (or L5-L6):
 - a. with the presence of demonstrable nerve root impingement,* as assessed by MRI;
 - b. chief complaint of unilateral radiculopathy** and/or radicular leg pain corresponding to the ipsilateral leg and distribution of the affected nerve root; and
 - c. positive result of Straight Leg Raise (SLR) test ($\leq 70^\circ$) on the ipsilateral leg corresponding to the pain and distribution of the affected nerve root. The SLR should be performed with the subject lying flat on his/her back, and the angle measured relative to the horizontal plane of the examining table.

*Judged first by the investigator, then confirmed by assessment of independent central image readers.

**Defined as a condition characterized by pain radiating to some or all portions of the ipsilateral L5 or S1 dermatomes, which may be accompanied by corresponding ipsilateral weakness, sensory loss, and/or (for S1 compression) decreased or absent ankle (Achilles) reflex.

4. Subjects with a current episode of radiculopathy that:
 - a. is symptomatic only in the unilateral leg and with a distribution corresponding to that of the affected nerve root, and
 - b. has been present for 6 weeks or more but 12 months or less, and
 - c. which is still ongoing at the time of informed consent.

Note: Subjects may have had similar past episodes involving the same nerve root; in this case, however, the most recent past episode must have ended at least 3 months prior to the onset of the current episode.

5. Subjects with inadequate improvement in pain caused by LDH despite 6 weeks or more of conservative treatment,* which is still ongoing at the time of informed consent.

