9.5.9 Neurologic Status

- Assessment Points: All Visits
- Item: SLR test [Positive ($\leq 70^\circ$) or Negative ($> 70^\circ$)], sensation [Yes, No for existence of hypoesthesia], muscle strength [Yes, No for existence of muscle weakness], and deep tendon reflex [Yes, No for existence of hyporeflexia]
- Method: Neurological examinations will be performed by the investigator, and the results will be documented.

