11.6.3 Other Secondary

All endpoints, including the primary and key secondary endpoints, will be summarized by treatment group and by time point. The differences of other secondary endpoints between the SI-6603 and control groups will be analyzed at each time point as below. In addition, weekly pain intensity scores will be summarized by treatment group.

- A similar longitudinal analysis model will be used as described in the primary efficacy analysis for the analysis of change from baseline in pain intensity scores, function scores, QOL scores, and volumes, by including the corresponding baseline value as the fixed effect instead of the baseline worst leg pain score.
- Neurologic status as determined by neurological examinations will be analyzed with a logistic regression model. Baseline neurologic status and duration of leg pain will be included as covariates.
- For the global assessments of PGIC score and CGIC score, responder analysis with the two best categories as “responder” will be analyzed with a logistic regression model. Baseline worst leg pain score and duration of leg pain will be included as covariates.
- Scores on the WPAI will be analyzed with the analysis of covariance model including the baseline value and duration of leg pain as covariates.
- The incidence of rescue medication use will be analyzed with Fisher’s exact test, and the amount of rescue medication use and usage of concomitant medications for LDH will be analyzed with the Wilcoxon rank sum test.
- Cumulative distribution of percentage change from baseline in worst leg pain and ODI will be generated, and differences between the SI-6603 and control groups in the percentages of subjects experiencing a >30% and >50% improvement in worst leg pain score will be analyzed with Fisher’s exact test.
- For the analysis of the percentages of responders by composite definition, differences between the SI-6603 and control groups in the percentages of positive responders will be analyzed with a logistic regression model. Baseline worst leg pain score and duration of leg pain will be included as covariates.
- Time to post-treatment surgery for LDH will be evaluated by survival analysis using the log-rank test.

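### The SAP replaces the protocol's baseline-adjusted logistic regression for binary secondary endpoints with unadjusted Z tests and does not declare the change

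*SAP*

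**What the plan says.** Protocol 11.6.3 names a model and its covariates for three groups of binary endpoints.

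- Neurologic status: "Neurologic status as determined by neurological examinations will be analyzed with a logistic regression model", and "Baseline neurologic status and duration of leg pain will be included as covariates".
- PGIC and CGIC response (two best categories): logistic regression, with "Baseline worst leg pain score and duration of leg pain will be included as covariates".
- Composite response: "differences between the SI-6603 and control groups in the percentages of positive responders will be analyzed with a logistic regression model", with the same two covariates as PGIC and CGIC.

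SAP 7.3.3.3 analyses all three without covariates. For neurologic status: "Neurologic status as determined by neurological examinations will be compared between treatments with a difference in proportions Z test". For the composite, differences "in the percentages of positive responders will be compared between treatments with a difference in proportions Z test". PGIC and CGIC are treated the same way. Each has Fisher's exact test as the fallback when an expected cell count is below 5, and a Wald interval for the difference. No logistic regression remains in the SAP.

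The same SAP section also moves rescue medication incidence and the 30% and 50% leg pain response rates from the protocol's Fisher's exact test to the Z test.

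SAP section 11 declares three changes: multiple imputation after a prohibited procedure, the multiplicity procedure, and the definition of recurrence of LDH. None of the binary-method changes appears there.

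**The concern.** There are two separate issues.

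The first is documentation. Protocol section 11 leaves detail to the SAP, but replacing a named model and dropping its covariates goes beyond detail. SAP section 11 already covers an other-secondary endpoint (recurrence), so its scope is not limited to primary and key secondary analyses. A reader relying on it would conclude that these binary analyses follow the protocol. The change is also uneven: SAP 7.3.3.3 keeps baseline and duration adjustment for WPAI and for the longitudinal models, and gives no reason for dropping it only for binary outcomes.

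The second is precision, mainly for sensation, strength and reflex. Protocol 4.1 makes these deficits optional at entry: radiculopathy is one "which may be accompanied by corresponding ipsilateral weakness, sensory loss, and/or (for S1 compression) decreased or absent ankle (Achilles) reflex". Subjects can therefore differ at baseline. Protocol 9.5.9 records each sign as present or absent, for example "muscle strength [Yes, No for existence of muscle weakness], and deep tendon reflex [Yes, No for existence of hyporeflexia". The endpoint in SAP 7.2 is the absolute state (free of the deficit), not change from baseline, so baseline status may well predict it. An unadjusted comparison ignores that information.

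The issue has little reach beyond those three outcomes.

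- **SLR:** it is positive at baseline in every eligible subject, so adjusting for it gains nothing.
- **PGIC, CGIC and composite:** the covariates are range-limited at entry (leg pain 50 to 90 mm, duration 6 weeks to 12 months), and the composite already scores neurologic status against baseline.
- **Strength:** it may vary less than the other two signs, because Protocol 4.2 excludes grades below 4.

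**Working it through.** **Text comparison**

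| Endpoint | Protocol 11.6.3 | SAP 7.3.3.3 | In SAP section 11? |
|---|---|---|---|
| Neurologic status | Logistic; baseline status, duration | Z test | No |
| PGIC/CGIC response | Logistic; baseline leg pain, duration | Z test | No |
| Composite response | Logistic; baseline leg pain, duration | Z test | No |
| Rescue incidence | Fisher | Z test | No |
| 30%/50% leg pain response | Fisher | Z test | No |

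**Possible loss of precision.** The plan has no figure of its own to reproduce here. From the documents: 160 per arm and 15% dropout, so n = 160 × 0.85 = 136 per arm. This fits the SAP's use of non-missing values as the denominator for neurologic status. Every rate below is assumed.

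Let d be the proportion with a deficit at baseline, s the probability that a subject without one stays clear, and r the probability that a deficit resolves (0.40 control, 0.60 active).

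- Proportion clear in an arm: p = (1 − d)s + d·r
- Raw variance: [p0(1 − p0) + p1(1 − p1)]/n
- Standardised risk difference: fit the logistic model m (treatment, baseline status), then average m1(x) − m0(x) over all subjects to get Δ. With 1:1 allocation and A the treatment indicator, the influence function is m1 − m0 − Δ + (A/0.5)(Y − m1) − ((1 − A)/0.5)(Y − m0). The variance is its mean square divided by 272.

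*Example 1: d = 30%, s = 97%.*

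- p0 = 0.7 × 0.97 + 0.3 × 0.4 = 0.799; p1 = 0.679 + 0.18 = 0.859; difference 0.06.
- Raw: (0.1606 + 0.1211)/136 = 0.002071, SE 0.0455, full 95% CI width 2 × 1.96 × 0.0455 = 17.8 points.
- Standardised: variance ratio 0.671, SE 0.0373, full width 14.6 points.
- Power: 26.1% raw, 36.3% standardised.

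*Example 2: d = 10%, s = 90%.*

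- p0 = 0.85, p1 = 0.87.
- Raw: (0.1275 + 0.1131)/136 = 0.001769, SE 0.0421, full width 16.5 points.
- Standardised: variance ratio 0.880, full width 15.5 points.

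| Assumed setting (sensation/strength/reflex) | Variance reduction | CI narrower by | Power gain (points) |
|---|---|---|---|
| Strong persistence: d 10–60%, s 90% or 97% | 12–33% | 6–18% | 0.4–13.7 |
| Weaker persistence: 80–90% clear without v 60–70% with a baseline deficit, treatment odds ratio 1.8, d 10–50% | 0.5–11% | 0.2–5% | 0.2–3.8 |
| Baseline does not predict outcome | 0 | 0 | 0 |

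The largest power gain is 46.8% to 60.5%, at d = 50% and s = 97%.

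*Rare weakness, d = 2–10%.* The interval is 6–15% narrower with s = 97% and 1–3% narrower under weaker persistence (90% v 60% clear). The power gain is at most 1.8 points. At d = 2% and s = 97%, about 136 × 0.039 ≈ 5 subjects per arm have a deficit at follow-up, close to the SAP's Fisher threshold.

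*Odds-ratio scale.* The adjusted log-odds SE is larger than the raw one: by 7–23% under strong and 0.2–6% under weaker persistence. In Example 1 it rises from 0.326 to 0.400, although z rises from 1.31 to 1.59 because the conditional log-odds ratio is also larger. The protocol's odds ratio alone would therefore not give a narrower interval. That gain needs the standardised risk difference.

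*Simulation check.* Nine settings of 2,000 runs, with duration as a second covariate, agreed with the closed form to within 0.03 in variance ratio in the seven settings computed both ways. Coverage was 94.1–95.6% (standardised) and 93.8–95.4% (raw). With no treatment effect, rejection was 4.8% and 5.3% (Z) and 5.2% and 5.2% (standardised).

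*PGIC, CGIC and composite, 160 per arm* (missing counts as non-response). With a log-odds ratio of 0.1–0.2 per SD for each covariate, variance falls 0.5–2% and power rises 0.2–0.7 points. At 0.4 per SD the figures are 6–7% and 2.7–2.8 points.

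**The case against.** The strongest reply is that the precision figures compare the SAP with an estimator found in neither document. The protocol promised a conditional odds ratio, whose interval would not have been narrower, so no interval precision promised by the protocol was lost. Power has little use for endpoints that SAP 7.3.4 says cannot be called significant. The assumed rates span everything from no gain to a one-third cut in variance. The quoted widths are full widths: as margins, the two examples go from about 8.2 to 7.7 and from 8.9 to 7.3 points. The raw difference with a Fisher fallback is simple and valid.

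Most of this stands as a limit on size. It is why the point is minor and why the section 11 listing is the minimum fix. It does not answer the undeclared replacement of a named method, which needs no assumption. Nor does it remove the case for adjusting sensation, strength and reflex for baseline status, which the protocol itself specified and which is already recorded.

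The reply also points to a further unlisted change. Protocol 11.8.4 counts as composite non-responders those who discontinue for LDH-related AEs or lack of efficacy and then have missing data. SAP 7.1.1 does so for everyone with missing data. This can alter the responder counts, and it belongs in the same list.

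**Conclusion.** The concern holds and is minor. The discrepancy between Protocol 11.6.3 and SAP 7.3.3.3, and its absence from SAP section 11, are plain on the text. Validity, type I error and the gatekept claims are unaffected.

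The precision cost is possible, not established. It depends on how common deficits are at entry and how strongly baseline status persists, and the documents give neither. On the assumed rates, the interval for sensation, strength or reflex could be up to 18% narrower with strong persistence, up to about 5% with weaker persistence, and no narrower if baseline carries no information. For PGIC, CGIC and composite response little gain is expected, and for SLR none from its baseline status.

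**What to change.** 1. In SAP 7.3.3.3, for sensation, muscle strength and deep tendon reflex, restore the protocol's logistic model (treatment, baseline status, duration of leg pain). Report from it a standardised risk difference with 95% CI. This adds to the protocol but keeps the SAP's difference scale. Keep raw counts and percentages as description, and Fisher's exact test where the model cannot be fitted.
2. Leave SLR with the Z test. Restoring the adjusted model for PGIC, CGIC and composite response is optional.
3. Before unblinding, list in SAP section 11, with reasons, every binary-endpoint method that still differs from the protocol. Include the move from Fisher to Z for rescue incidence and 30%/50% response, and the composite non-responder rule. If the Z tests are kept throughout, this listing is the minimum fix.

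The cost is SAP wording and standard code; every covariate is already collected. The downside is model-based output with a sparse-data fallback: in the simulations the model failed to fit in 0–3.2% of data sets (worst case 63 of 2,000, at 60% deficit and 97% staying clear).

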8.1.3 Other Secondary

The other secondary efficacy endpoints for this study are as follows:

- Change from baseline in worst leg pain score at each time point
- Change from baseline in worst low back pain score at each time point
- Change from baseline in ODI score at each time point
- Percentage of subjects with negative SLR test
- Percentage of subjects without hypoesthesia, muscle weakness or hyporeflexia
- Patient Global Impression of Change (PGIC) score at each time point
- Clinical Global Impression of Change (CGIC) score at each time point
- Change from baseline in 36-item Short Form Health Survey (SF-36) scores at each time point
- EuroQol Group 5-Dimension Quality of Life instrument, 5-level version (EQ-5D-5L) quality of life (QOL) score and VAS score at Week 13 and Week 52
- Work Productivity and Activity Impairment Questionnaire (WPAI) score at Week 13 and Week 52
- Incidence and amount of rescue medication use over 13 weeks
- Change from baseline in amount of rescue medication use at each time point
- Cumulative distribution of percentage change from baseline in worst leg pain score at Week 13 and Week 52

- Cumulative distribution of percentage change from baseline in ODI score at Week 13 and Week 52
- Responder rate by composite definition^{*1} at Week 13
- Change from baseline in intervertebral disc volume at Week 13 and Week 52
- Change from baseline in herniation volume at Week 13 and Week 52
- Incidence of post-treatment surgery for LDH at the same level of investigational product injection
- Number of subjects with recurrence of LDH^{*2} at Week 52

*1 A subject who meets all 4 criteria below (A, B, C, and D) as assessed at Week 13:

- A. A reduction of 30% in worst leg pain score during the past 24 hours assessed by VAS from baseline to Week 13;
- B. Improvement of 30% in ODI score from baseline to Week 13;
- C. Maintenance or improvement of neurologic status (motor, sensory, reflexes) from baseline to Week 13; and
- D. No “Treatment Failure”

“Treatment Failure” is defined as a subject to whom any of the conditions shown below become applicable until Week 13 after investigational product injection:

- i. Use of additional medication/therapy to treat TEAEs or complications associated with LDH
 - New prohibited medications used for more than 7 days;
 - Increase of restricted medications used for more than 7 days;
 - Use of new prohibited therapies; or
 - Increase in frequency or intensity of restricted therapies.

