7.2 Efficacy Variables

The primary efficacy outcome is the change from baseline in the weekly averages of the VAS worst leg pain assessed at Weeks 1, 2, 4, 6, 13, 26, 39, and 52. Baseline is defined as the average of the 7 daily worst pain measures leading up to the randomization visit.

Key secondary outcomes include:

- Change from baseline to Week 13 in herniation volume
- Change from baseline to Week 13 in ODI score
- Change from baseline to Week 52 in average worst leg pain score during the past 24 hours over the previous 7 days, as assessed by 100 mm VAS.

Supportive outcomes include:

- Change from baseline in worst leg pain score at each time point
- Change from baseline in worst back pain score at each time point
- Change from baseline in ODI score at each time point
- Percentage of subjects with negative SLR test at each time point
- Percentage of subjects without hypoesthesia, muscle weakness or hyporeflexia at each time point
- Patient Global Impression of Change (PGIC) score at each time point
- Clinical Global Impression of Change (CGIC) score at each time point
- Change from baseline in SF-36 scores at each time point
- EQ-5D-5L (EuroQol Group 5-Dimension Quality of Life instrument, 5-level version) quality of life (QOL) score and VAS score at Week 13 and Week 52
- WPAI score at Week 13 and Week 52
- Incidence and amount of rescue medication use over 13 weeks
- Change from baseline in amount of rescue medication use at each time point
- Cumulative distribution of percentage change from baseline in worst leg pain score at Week 13 and Week 52
- Cumulative distribution of percentage change from baseline in ODI score at Week 13 and Week 52
- Responder rate by composite definition at Week 13
- Change from baseline in intervertebral disc volume at Week 13 and Week 52
- Change from baseline in herniation volume at Week 13 and Week 52
- Incidence of post-treatment surgery for LDH at the same level of investigational product injection
- Number of subjects with recurrence of LDH at Week 52

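### The SAP compares sensation, strength and reflex deficits over all subjects without baseline adjustment, so subjects normal at entry dilute any recovery difference, and recovery and new deficits are not separated

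*SAP*

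**What the plan says.** **Endpoint.** Protocol 8.1.3 defines it as "Percentage of subjects without hypoesthesia, muscle weakness or hyporeflexia". SAP 7.2 has "Percentage of subjects without hypoesthesia, muscle weakness or hyporeflexia at each time point". Protocol 9.5.9 records each item as present or absent: "sensation [Yes, No for existence of hypoesthesia], muscle strength [Yes, No for existence of muscle weakness", with reflexes handled the same way.

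**Analysis in the SAP.** Section 7.3.3.3 states: "Neurologic status as determined by neurological examinations will be compared between treatments with a difference in proportions Z test", with Fisher's exact test when expected counts are low. It names the items ("Outcomes will include SLR test, sensation, muscle strength, and deep tendon reflex") and the denominator ("Percentages will be reported out of non-missing values"). Baseline status enters neither as a filter nor as a covariate.

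**Analysis in the protocol.** Section 11.6.3 specifies logistic regression: "Baseline neurologic status and duration of leg pain will be included as covariates". SAP section 11, which lists departures from the protocol, does not mention that this model was replaced.

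**Entry.** Protocol 4.1 describes radiculopathy as pain "which may be accompanied by corresponding ipsilateral weakness, sensory loss, and/or (for S1 compression) decreased or absent ankle (Achilles) reflex". No deficit is required, and exclusion 21 removes weakness graded below 4 on the Medical Research Council scale. A positive straight leg raise, by contrast, is required of every subject.

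**Status.** These are other secondary endpoints. SAP 7.3.4 allows their p-values to be reported but not to be called statistically significant.

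**The concern.** A subject with normal sensation at entry has no sensory deficit to recover from, yet is counted as deficit-free at each visit unless a deficit develops. The percentage compared between arms therefore mixes three things: how many subjects were normal at entry, how many deficits resolved, and how many new ones appeared. With an unadjusted test nothing separates them.

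Two consequences follow. A real difference in recovery can look small because it is spread over subjects who could not show it. And high percentages in both arms can read as good recovery when they largely describe normal baseline examinations. Baseline sensation, strength and reflex status is not among the characteristics listed in SAP 6.1, so a reader may not see the starting point.

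Straight leg raise is not affected, because everyone should be positive at entry.

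**Working it through.** **Evaluable subjects.** The plan gives no power for these endpoints, so I take the number from the primary calculation (SAP 2.6: difference 12 mm, SD 30 mm, power 90%, two-sided 5%, dropout 15%).

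- n per arm = 2 × (1.960 + 1.282)² × 30² / 12² = 131.3, so 132.
- 132 / 0.85 = 155.3, so 156 per arm and 312 in total, consistent with the planned 320.
- 160 × 0.85 = 136 evaluable per arm.

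**Dilution.** Let f be the share with the deficit at baseline and p the share of those who have recovered by the visit. With no new deficits, the all-subject percentage is (1 − f) + f·p, so the between-arm difference is f × (p_active − p_control). Neither f nor p is in the documents; both are assumed below and shown as ranges.

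**Power** for a two-proportion Z test is Φ[(d − 1.96·SE0)/SE1], with SE0 pooled and SE1 unpooled. Example with f = 0.3 and recovery 60% v 40%:

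- All subjects: 0.70 + 0.3 × 0.6 = 0.88 v 0.70 + 0.3 × 0.4 = 0.82. SE0 = √(0.85 × 0.15 × 2/136) = 0.0433; SE1 = √[(0.1056 + 0.1476)/136] = 0.0431. Power = Φ[(0.06 − 0.0849)/0.0431] = 28%.
- Subjects with the deficit, 136 × 0.3 = 40.8 per arm: SE0 = √(0.25 × 2/40.8) = 0.1107; SE1 = √(0.48/40.8) = 0.1085. Power = Φ[(0.20 − 0.2170)/0.1085] = 44%.

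| f | All-subject rates | Difference | Power, all subjects | Power, deficit at baseline |
|---|---|---|---|---|
| 20% | 92% v 88% | 4 points | 19% | 31% |
| 30% | 88% v 82% | 6 points | 28% | 44% |
| 40% | 84% v 76% | 8 points | 38% | 55% |
| 60% | 76% v 64% | 12 points | 58% | 73% |

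With recovery 85% v 70% the loss is smaller: 31.5% v 36.6% at f = 30%, and 58.5% v 63.3% at f = 60%.

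**What baseline adjustment recovers.** A test stratified by baseline deficit serves as a stand-in for the protocol's logistic model. Simulated power (20,000 trials per setting, recovery 70% v 50%):

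| New deficits, both arms | f | Unadjusted, all | Deficit subset | Stratified, all |
|---|---|---|---|---|
| 0% | 30% | 33.2% | 45.6% | 45.2% |
| 0% | 50% | 54.7% | 66.5% | 66.3% |
| 0% | 70% | 73.0% | 80.3% | 80.2% |
| 5% | 30% | 27.7% | 45.9% | 32.8% |
| 5% | 50% | 50.8% | 66.4% | 58.4% |
| 5% | 70% | 72.5% | 80.8% | 77.6% |

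With no new deficits, adjustment recovers nearly all of the loss while keeping every subject. With 5% new deficits it recovers part of it.

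**If treatment changes new deficits.** Assume 10% new deficits on control and 5% on active, recovery 60% v 40%. At f = 20% the rates are 0.8 × 0.95 + 0.2 × 0.6 = 0.88 and 0.8 × 0.90 + 0.2 × 0.4 = 0.80, a difference of 8 points rather than 4. Power is then 44% over all subjects v 31% in the deficit subset. At f = 30% the difference is 9.5 points and power 50% v 44%; at f = 40%, 56% v 55%. The ranking can reverse.

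**The case against.** The percentage free of a deficit at a visit is a legitimate prevalence measure. It reflects both recovery and onset, and onset matters here: protocol 1.2.1.5 lists nerve damage among the injection risks, and protocol 12.4 names significant neurologic deficit among possible grounds for termination. Restricting the comparison to subjects with a baseline deficit would hide onset. This objection stands, and the fix has to keep both components.

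A reader might infer that any treatment effect is shrunk to the baseline fraction, or that the denominator alone is at fault. The documents do not support either. Exact shrinkage needs treatment to leave new deficits unchanged. The protocol also kept all subjects and adjusted for baseline, which in the simulation recovers nearly all the power when there are no new deficits. Much of the loss therefore comes from dropping that adjustment.

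It can also be said that SAP 7.3.3.3 summarises endpoints by time point, so baseline percentages may appear, and that the composite responder in SAP 7.3.3.4 already judges neurologic status against baseline. Both reduce the interpretive harm. Neither gives a between-arm estimate of recovery or of onset for the separate items.

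Finally, the prevalence and recovery rates above are assumptions, and milder ones cost only a few points of power.

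**Conclusion.** The point holds in limited form. The SAP compares three deficit items over all examined subjects without using baseline status, although entry requires none of the deficits, and it replaces the protocol's baseline-adjusted model without listing the change.

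If treatment does not affect new deficits, the reported difference is the recovery difference times the baseline prevalence. At 136 per arm and 60% v 40% recovery, the loss against the deficit subset is 16 power points at 30% prevalence (28% v 44%) and 15 at 60% (58% v 73%). At 85% v 70% recovery it is about 5 points at either prevalence. If treatment does change onset, the all-subject difference can be larger or smaller than this product.

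A reader might infer that the trial could miss a significant neurologic benefit. That goes too far: no power is claimed for these endpoints, and SAP 7.3.4 rules out calling their results significant. What suffers is the estimate and what a clinician can learn from it.

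**What to change.** For sensation, muscle strength and deep tendon reflex in SAP 7.3.3.3:

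1. Restore the protocol's logistic regression over all subjects, with baseline neurologic status and duration of leg pain as covariates. Name a fallback, such as a test stratified by baseline deficit, in case no subject normal at baseline develops a deficit and the baseline coefficient cannot be estimated.
2. At each visit report, by arm with the difference and 95% CI, (a) the percentage recovered among subjects with that deficit at baseline and (b) the percentage with a new deficit among those without it.
3. Add baseline status of the three items to SAP 6.1.
4. If the protocol's model is not restored, record and justify its removal in SAP section 11.

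The cost is SAP wording and a baseline split in the program. The examination is already done at Visit 2 before randomization (protocol 9.2.2), so both subset comparisons remain randomized ones. The downside is smaller denominators and wider intervals. Cells may be sparse, especially for strength because of exclusion 21; the SAP's existing Fisher's exact rule covers the tests.
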